4.5.3. Additional Safety Assessments

Cardiovascular events

The following cardiovascular events on treatment will be summarised and listed:

- Myocardial infarction/unstable angina
- Congestive heart failure
- Arrhythmias
- Valvulopathy
- Pulmonary hypertension
- Cerebrovascular events stroke and transient ischemic attack
- Peripheral arterial thromboembolism
- Deep vein thrombosis/pulmonary embolism
- Revascularization

Laboratory Data

The change from baseline values on- and post- treatment for clinical chemistry and haematology will be summarised. Summaries of the data outside the normal range and the changes from baseline relative to the normal range will also be produced, including 'any time post-baseline', which will include laboratory assessments taken at scheduled, unscheduled and Early Withdrawal visits and will report the most extreme value(s). Data from subjects who have values outside the normal range will be listed.

Urinalysis results (screening only) will be listed.

Vital Signs

Pre-dose systolic blood pressure, diastolic blood pressure and pulse rate including change from baseline for on- and post- treatment will be summarised and listed.

ECG

Actual and change from baseline (for post-baseline timepoints) values for QTc(F) and heart rate including on- and post- treatment will be summarised by treatment for Baseline, Week 24, Week 52 and Withdrawal visit. ECG results will also be listed. Abnormal findings and interpretations will be listed separately.

Individual maximum QTc(F) values will also be summarised to show the number of subjects with maximum values (msec) in the following categories:

- ≤ 450
- $450 < \text{to } \leq 480$
- $480 < \text{to } \leq 500$
- > 500

Additionally, individual maximum changes from baseline in QTc(F) values will be summarised to show the number of subjects with maximum changes (msec) in the following categories:

- Increase of <=30 msec
- Increase of >30-<=60 msec
- Increase of >60 msec

Liver Event

Liver event information on- and post- treatment will be summarised and all subjects who report a liver event will be listed.

Immunogenicity

For the immunogenicity assessment, two types of anti-drug antibody (ADA) assays will be performed: a binding antibody assay and a neutralizing antibody assay (NAb).

For the binding assay, there will be a three-tiered analysis: screening, confirmation and titration. The screening assay produces a result of positive or negative relative to a screening cut point. Positive samples continue with the confirmation assay, which also produces a result of positive or negative relative to a confirmation cut point. For positive confirmation samples, a titre value will also be obtained to quantify the degree of binding in a titration assay, and the sample will be tested with the neutralizing antibody assay, which also reports results as positive or negative. A sample that is positive in the confirmation assay is considered positive for anti-SB-240563 antibodies.

A table will be produced summarising results for the ADA assay in the mITT Population. The highest binding ADA assay confirmatory result obtained post-baseline for a participant (including both on-treatment and post-treatment data, unscheduled and early withdrawal visits), will be summarised with a positive result being considered higher than a negative one, participants with both positive and negative results will be identified in the positive category. Descriptive statistics for titre results will also be presented. In addition, the highest NAb assay result during the same period will be summarised (again with a positive result being considered higher than a negative one and participants with both positive and negative results will be identified in the positive category).

All ADA results (i.e. screening and confirmatory assay results, titre values) will be listed.

A listing will also be produced results for the neutralising antibody assay in the mITT Population, by treatment group and visit. Neutralising antibody assay results will be categorised as follows:

1. Negative
2. Positive

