7.1.3. Critical procedures performed at randomization (Visit 2)

- Vital signs
- Review of randomization criteria, and data collected at screen including verification of eosinophilic asthma
- Pulmonary function tests and assessment of reversibility (If reversibility was not achieved at Visit 1, the procedure may be repeated at this visit and this is needed to qualify the subject for randomization). (See Section [7.2.4](#))
- Review eDiary data including PEF diurnal variability (see Section [7.2.2](#))
- Asthma Control Questionnaire (ACQ-5) (see Section [7.2.5](#))
- St George's Respiratory Questionnaire (SGRQ) (see Section [7.2.3](#))
- Laboratory tests:
 - Haematology with differential
 - Blood for baseline immunogenicity, PK
 - Urine pregnancy test for females of child bearing potential

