7.3.5. Immunogenicity

Blood samples will be collected for the determination of anti-mepolizumab antibodies, prior to dosing on dosing days, as detailed in the Schedule of Activities (Section 1.2). A PK sample will be collected at the time of the immunogenicity sample collection (for subjects in the PK sub-study this can be the sample collected for PK assessment). For subjects who are ADA or NAB positive, PK samples will be assessed.

Details for sample collection and processing may be found in the SRM.

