1.1. Objectives, Estimands and Endpoints

Objectives	Endpoints
Primary	
 To evaluate the efficacy of mepolizumab 100 mg subcutaneous (SC) every 4 weeks versus placebo on the frequency of clinically significant exacerbations in adult and adolescent Chinese subjects with severe asthma with eosinophilic airway inflammation. 
Frequency of clinically significant exacerbations of asthma over the 52-week treatment period. Clinically significant exacerbations are defined as: Worsening of asthma which requires use of systemic corticosteroids and/or hospitalizations and/or Emergency Department (ED) visits.
 
For all subjects, oral corticosteroid for at least 3 days or a single IM Corticosteroid (CS) dose is required. For subjects on maintenance systemic corticosteroids, at least double the existing maintenance dose for at least 3 days is required.

Secondary	
 To evaluate the effects of mepolizumab compared with placebo on a range of clinical markers of asthma control, including exacerbations, lung function, and quality of life. 
 Time to first clinically significant exacerbations Mean change in St. George's Respiratory Questionnaire (SGRQ) at Week 52 Frequency of exacerbations requiring hospitalisation (including intubation and admittance to an ICU) or ED visits over the 52-week treatment period Frequency of exacerbations requiring hospitalisation over the 52-week treatment period Mean change from baseline in clinic pre-bronchodilator FEV1 at Week 52
Safety	
 To evaluate the safety and tolerability of mepolizumab compared with placebo, in subjects with severe asthma with 
 Adverse Event including systemic (i.e. allergic [type I hypersensitivity] and Other systemic) and injection site reactions reported throughout the 52-week treatment period Haematological and clinical chemistry parameters

Objectives	Endpoints
eosinophilic inflammation	
 • Vital signs (pulse rate and systolic and diastolic blood pressure) • 12-lead ECG • Frequency of subjects with anti-mepolizumab antibody positive results
Others	

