4.5.2. Adverse Events

Adverse events will be summarized by system organ class and preferred term . AEs will be summarized for on-treatment period, unless otherwise specified.

The number and percentage of subjects experiencing at least one AE during on-treatment period of any type, AEs within each body system and AEs within each preferred term will be summarized for each treatment group.

- Overview of all AEs

The following summary tables will be produced:

- Summary of all AEs; (on-treatment, post-treatment)
- Summary of drug related AEs;
- Summary of Common ($\geq 3\%$ Incidence in any Treatment Group) Adverse Events by Overall Frequency
- Summary of AEs by maximum intensity
- Summary of Severe AEs (on-treatment, post-treatment)
- Summary of SAEs; (on-treatment, post-treatment)
- Summary of non-SAEs
- Summary of Common ($\geq 3\%$ Incidence in any Treatment Group) Non-Serious Adverse Events by Overall Frequency (on-treatment)
- Summary of drug related SAEs (on-treatment)
- Summary of non-fatal SAEs (on-treatment)
- Summary of Fatal Events (on-treatment, post-treatment)
- Summary of Adverse Events Leading to Permanent Discontinuation of Study Drug or Withdrawal from Study
- Summary of Adverse Events Leading to Interruption of Study Drug
- Summary of AEs by ADA Assay Result Category (On-Treatment)
- Summary of AEs by NAb (On-Treatment)

The following listings will be produced:

- Listing of Subject Numbers for Individual Adverse Events
- Listing of all Adverse Events
- Listing of Non-Fatal Serious Adverse Events
- Listing of Fatal Adverse Events
- Listing of Adverse Events Leading to Discontinuation of Investigational Product and/or Withdrawal from the Study

Exposure Adjusted Rate for Adverse Events

Exposure adjusted rate for adverse events represents the frequency of events per 1000 subject-years of exposure, which is calculated as:

(Total number of adverse events / Total Duration of Exposure in days)/365.25*1000

The summary of exposure adjusted for the events below will be provided:

- All Adverse Events (on treatment)
- Most frequent AEs reported by 3% or more subjects (on treatment)
- Drug related AEs (on treatment)
- Non-fatal SAEs (on treatment)

- Adverse Events Leading to Permanent Discontinuation of Study Drug or Withdrawal from Study (on treatment)

Adverse Events of Special Interest

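### The ADA and NAb summaries leave out the baseline sample, so they cannot separate pre-existing antibodies from those that emerge or are boosted on treatment

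*SAP*

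**What the plan says.** The safety endpoint in SAP 1.1 is "Frequency of subjects with anti-mepolizumab antibody positive results". Protocol 9.4.2.5 adds only that the data will be summarised descriptively.

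The working rule is in SAP 4.5.3, under Immunogenicity:

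- Sample level: "A sample that is positive in the confirmation assay is considered positive for anti-SB-240563 antibodies". Confirmed positives also receive a titre and a NAb test.
- Participant level: the table takes "The highest binding ADA assay confirmatory result obtained post-baseline for a participant", pooling on-treatment, post-treatment, unscheduled and early-withdrawal samples; "participants with both positive and negative results will be identified in the positive category".
- For NAb, "the highest NAb assay result during the same period will be summarised".
- Titres are described, and all ADA results are listed. NAb results are listed by treatment group and visit.

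The baseline sample exists. Protocol 7.1.3 includes "Blood for baseline immunogenicity, PK" among the Visit 2 procedures, and Protocol 7.3.5 says: "Blood samples will be collected for the determination of anti-mepolizumab antibodies, prior to dosing on dosing days". The general baseline rule in SAP 4.1.2 (last non-missing value before the first dose) would give each participant a baseline ADA status.

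SAP 4.5.2 also plans adverse event tables split by ADA result category and by NAb. It does not define the categories.

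**The concern.** A baseline antibody sample serves to tell a reaction that predates the drug from one that follows it. Under the SAP rule it contributes to no specified summary and reaches only the listings. Neither document defines treatment-emergent or boosted ADA.

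Information is lost in two ways. A participant with unchanged pre-existing reactivity looks like a converter. A participant who was positive at baseline and whose titre climbs on drug is not picked out, although titres are available. Protocol 5.2 (exclusion 21) bars anyone who received investigational product in an earlier mepolizumab study, so a positive at Visit 2 should not come from earlier trial dosing.

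What is at stake is how far a named safety endpoint can be interpreted, and possibly the adverse event tables by antibody status. The primary and secondary efficacy analyses are not affected.

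**Working it through.** The plan states no expected ADA rate, so there is no figure to reproduce. The check has two parts.

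**1. What the rule does to each type of participant**

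| Baseline | Post-baseline | SAP 4.5.3 category | With baseline used |
|---|---|---|---|
| Negative | Any positive | Positive | Treatment-emergent |
| Positive | Any positive, titre not raised | Positive | Pre-existing |
| Positive | Any positive, titre raised | Positive | Boosted |
| Positive | All negative | Negative | Pre-existing, not persisting |
| Negative | All negative | Negative | Negative |

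The first three rows fall into one category.

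**2. How large the excess could be**

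Inputs:

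- n = 150 per arm (Protocol 4.3, planned).
- b = baseline prevalence, s = share of baseline positives with at least one post-baseline positive, t = incidence among baseline negatives. All three are assumptions.

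Formulae:

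- Treatment-emergent count = n(1 − b)t
- SAP count = n(1 − b)t + n·b·s
- Excess of the SAP count = n·b·s

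| b | s = 0 | s = 0.5 | s = 1 |
|---|---|---|---|
| 0% | 0 | 0 | 0 |
| 1% | 0 | 0.75 | 1.5 |
| 2% | 0 | 1.5 | 3 |
| 5% | 0 | 3.75 | 7.5 |

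Example with b = 2%, s = 1, t = 2%: treatment-emergent = 150 × 0.98 × 0.02 = 2.94 (1.96%). The SAP row = 2.94 + 150 × 0.02 × 1 = 5.94 (3.96%).

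The excess counts every baseline positive who is positive again, including any who were boosted. It is therefore the number the table cannot classify, not the number unrelated to the drug.

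**Placebo column in the same example.** If b and s are equal in both arms and placebo has no new positives, placebo shows 3 on average, and the difference between arms is 5.94 − 3 = 2.94, the treatment-emergent count. That holds only in expectation. The number of baseline positives per arm has a binomial standard deviation of √(150 × 0.02 × 0.98) = 1.71, so the chance difference between arms has a standard deviation of about 1.71 × √2 = 2.4, close to the 2.94 being sought.

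**The case against.** The best defence is that the SAP delivers the endpoint as written. The endpoint counts subjects with positive results and does not say treatment-emergent, and the protocol promises only descriptive statistics. This stands: no passage is contradicted.

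Second, both arms are tabulated and randomisation is 1:1, so pre-existing positivity should appear about equally under placebo. A reader might infer that the plan overstates drug-induced immunogenicity. The documents do not support that as a flat statement, because it holds only if the mepolizumab column is read alone. The placebo column still cannot classify an individual or show boosting, and with few positives it corrects the frequency only roughly.

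Third, the listings keep each result, so converters can be traced by hand. This is true, but it leaves the classification unspecified and done after the event.

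Fourth, a reader might infer that everyone positive before dosing will be reported as positive on mepolizumab. That goes too far: a baseline positive whose later samples are all negative is reported negative.

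Fifth, the adverse event tables by antibody status may or may not inherit the rule. Their categories are undefined, so a claim that they mix pre-existing and induced positives is inference.

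Finally, every rate in the illustration is assumed. Protocol 2.3.1 describes the immunogenic potential as low and reports no link between ADA and specific adverse events.

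**Conclusion.** The point holds in a limited form. The ADA and NAb summaries ignore a baseline result that is collected, so they cannot separate pre-existing, treatment-emergent and boosted antibodies, and positivity cannot be attributed to mepolizumab for individual subjects. This limits interpretation; it is not a conflict with the endpoint and not a demonstrated bias.

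The size is unknown and could be zero. Over assumed prevalence of 0-5% and persistence of 0-100%, the excess is 0 to 7.5 subjects per 150. It matters most when treatment-emergent cases are few, since a handful of baseline positives could then make up much of the row. It is worth correcting because the data are already planned and the correction is small.

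**What to change.** In SAP 4.5.3:

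- Keep the present row (any post-baseline positive), so that it stays available for comparison.
- Add, by arm, baseline ADA status cross-tabulated with the highest post-baseline result, showing missing baselines separately.
- Define treatment-emergent ADA as baseline negative or missing with a post-baseline positive.
- Define titre-boosted ADA as baseline positive with a pre-specified rise in titre. The documents give no threshold, so the sponsor must set one.
- Add a treatment-emergent row for NAb. The NAb assay reports only positive or negative, so a boosted row does not apply.

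In SAP 4.5.2, state which ADA and NAb categories the adverse event tables use, and show treatment-emergent status there.

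Settle the definitions before unblinding. The cost is SAP wording, one more table dimension and some small cells; no extra samples, assays or visits are needed.

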4.6. Pharmacodynamic Analyses

Blood eosinophils on treatment will be summarised by treatment group and visit.

Ratio to baseline at W52 will be analysed using a mixed model repeated measures (MMRM) analysis adjusting for covariates of treatment group, baseline, baseline

maintenance oral corticosteroids (OCS vs no OCS), baseline % predicted pre-bronchodilator FEV1, exacerbations in the year prior to the study (as an ordinal variable (2, 3, 4+)), visit, plus interaction terms for visit by baseline and visit by treatment group. Blood eosinophil counts will be log transformed (log_e) prior to analysis. The log transformation for values of 0 GI/L will be based on a value of 0.005 GI/L. Data will be log-transformed prior to analysis. Visit will be fitted as a categorical variable with the effect of treatment group and baseline varying at each visit (i.e. visit by baseline and visit by treatment group interactions will also be included in the model).

To assess the robustness of Blood eosinophils results from the impacts of missing dose, the summary of blood eosinophils without missing dose will also be provided. If the subject has dose missing, the data after the first missing dose will be excluded.

4.7. Pharmacokinetic Analyses

4.7.1. Pharmacokinetic Concentration

Concentrations will be determined at a number of time points over the whole treatment period, ranging from the first dose to last dose when steady state was achieved (Protocol Table 1).

To minimize the potential impact of missing dose on observed plasma concentrations, only the mepolizumab plasma concentrations for which no missing dose occurring within approximate 5 half-life prior to the time of the SC administration will be summarized by visit, i.e., the concentrations at V2-1, V2-2 and V3 without missing dose at V2; the concentrations at V8 without missing dose at V4-7, the concentrations at V14 without missing dose at V10-V13 and the concentrations at V14-1 to V15-2 without missing dose at V10-V14. Standard summary statistics will be calculated (i.e. mean, standard deviation, median, minimum, and maximum).

All the records of concentrations will be listed. Individual concentration-time profiles and median/mean profiles with all records will be plotted on both a linear and semi-log scale.

Protocol amendment 4 updated Study Day of V2-1 (from day 7 to day 8) and V2-2 (from day 14 to day15) to clarify the duration of PK sample collection in Section 1.2 of protocol. On final PK Sample ID form and related PK CRF forms in InForm System, “VISIT 2 PREDOSE” refers to “VISIT2 DAY1”, “VISIT 2 DAY7” refers “VISIT 2 DAY8”, and “VISIT 2 DAY 14” refers to “VISIT 2 DAY15” in SoA.

Concentrations that are below the LLQ (“lower limit of quantification”) are listed as NQ in the raw concentration data. For NQ at pre-dose at V2, it will be imputed as 0, for post first dose records, NQ will be imputed as NULL.

4.7.2. Pharmacokinetic Parameters

The pharmacokinetic parameters for PK data collected following the first dose (up to Day 28/ Visit 3) and at steady state (i.e., at Visit 14 and 15) will be calculated by standard

non-compartmental analysis according to current working practices and using Phoenix WinNonlin, version 6.3 or above.

- Pharmacokinetic parameters described in [Table 1](#) will be calculated, if data permits. Particularly some directly determined parameters, e.g., Cmax or Tmax, might not be reported if the data are considered insufficient to produce.
- All non-compartmental parameters will be calculated based on actual sampling times.

Table 1 **Derived Pharmacokinetic Parameters**

Parameter	Parameter Description
AUC(0- τ)	Area under the concentration-time curve during the dosing interval at steady-state, i.e., 4 weeks for the study
AUC(0- t)	Area under the concentration-time curve for the last dose, will be calculated from predose on Visit 14 to the time of the last quantifiable concentration (C(t)) based on data collected after last dose, using the linear trapezoidal rule for each incremental trapezoid and the log trapezoidal rule for each decremental trapezoid
Cmax	Maximum observed concentration after single dose, determined directly from the concentration data collected after the first dose
Cmax_ss	Maximum observed concentration at steady state, determined directly from the concentration data collected after last dose at Visit 14.
Cavg_ss	Averaged concentration during the dosing interval at steady state, i.e., 4 weeks for the study
Tmax	Time to reach Cmax after single dose, determined directly from the data collected after the first dose
Tmax_ss	Time to reach Cmax at steady state, determined directly from the data collected after last dose at Visit 14
Ctrough	Trough concentration prior to dose at Visit 3
Ctrough_ss	Trough concentration prior to dose at steady-state (Visit 14)
t $\frac{1}{2}$	Apparent terminal half-life will be calculated as (just for data collected after last dose at Visit 14): $t\frac{1}{2} = \ln(2) / \lambda_z$
CL_ss/F	Apparent Clearance at steady state, calculated as: CL_ss/F = Dose / AUC(0- τ)
Vz/F	Apparent volume of distribution based on the terminal phase observed after last dose at Visit 14
λ_z , lambda_z	Terminal phase rate constant

All derived pharmacokinetic parameters described above will be summarised and listed. The parameters of Cmax, Tmax and Ctrough will be summarized at Visit 2, the rest of parameters in table 1 will be summarized at Visit 14. For each of these parameters the following summary statistics will be calculated: n, mean, 95% confidence interval for the mean, standard deviation, median, minimum, maximum, between coefficient of variation, geometric mean, 95% confidence interval for the geometric mean and standard deviation of log-transformed data. No statistical tests will be performed.

Between subject coefficient of variation (%CVb) for log-transformed data will be calculated according the following methods.

$$\%CVb = \text{SQRT}(\exp(SD^2) - 1) * 100$$

Where SD is the standard deviation of the log-transformed data.

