4.7.3. Assessment of Accumulation Ratio

To assess the extent of accumulation following mepolizumab multiple doses, the observed accumulation ratio (Ro) for mepolizumab will be determined as ratio of Cmax_ss (Cmax observed after last dose) to Cmax (Cmax observed after the first dose) and ratio of Ctrough_ss (Ctrough before the last dose) to Ctrough (Ctrough after the first dose)

$$Ro(Cmax) = Cmax_ss / Cmax$$

$$Ro(Ctrough) = Ctrough_ss / Ctrough$$

Accumulation ratios of Cmax and Ctrough will be summarised using n, mean, 95% confidence interval for the mean, standard deviation, median, minimum, maximum, between coefficient of variation, geometric mean, 95% confidence interval for the geometric mean and standard deviation of log-transformed data, and listed.

This pharmacokinetic statistical analysis will only be performed if sufficient data are available.

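### The missed-dose rule in SAP 4.7.1 covers the concentration summaries but is not carried into the steady-state parameters (4.7.2) or accumulation ratios (4.7.3) built from the same samples

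*SAP*

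**What the plan says.** SAP 4.7.1 gives its reason first, "To minimize the potential impact of missing dose on observed plasma concentrations", and then limits the by-visit summaries to "only the mepolizumab plasma concentrations for which no missing dose occurring within approximate 5 half-life prior to the time of the SC administration". It spells the rule out by visit. For the later samples it summarises "the concentrations at V14 without missing dose at V10-V13" and "the concentrations at V14-1 to V15-2 without missing dose at V10-V14". All concentrations are still listed.

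SAP 4.7.2 derives the parameters from those samples. It identifies steady state by visit (14 and 15), not by dosing history. Table 1 takes Ctrough_ss from the pre-dose sample at Visit 14 and computes CL_ss/F as dose divided by AUC(0-τ). Calculation depends on the data allowing it. The summary statement is "All derived pharmacokinetic parameters described above will be summarised and listed".

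SAP 4.7.3 summarises Ro(Cmax) and Ro(Ctrough) if there are sufficient data. Neither section mentions missed doses.

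**The concern.** The SAP treats a recent missed dose as reason enough to leave a concentration out of a summary, yet summarises quantities computed from that concentration without the same condition. For Ctrough_ss one measurement could be left out of the concentration table and kept in the parameter table, so the study report would show two different counts and means for one quantity, with no reason given.

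The parameter estimates are the only endpoint of the PK sub-study (protocol 3.1). CL_ss/F as dose over AUC(0-τ) holds only at steady state, and an accumulation ratio means little if its numerator follows a dosing gap. A subject off drug could also supply a Visit 14 sample: protocol 5.5 asks that subjects who stop treatment be followed where possible, and requires them to leave the sub-study only if they leave the main study.

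**Working it through.** **Does another section close the gap?**
- PK population (SAP 3, protocol 9.3.1): one dose and one analysed sample suffice; no rule on missed doses.
- SAP 6.2.13: the exclusion for two or more consecutive missed doses applies to the per-protocol population only.
- SAP 4.6: the rule that drops data after the first missed dose is for an extra eosinophil summary.
- SAP 4.7.4 and protocol 9.4.3: population PK is optional; the SAP leaves it to a separate plan.

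None of these covers 4.7.2 or 4.7.3.

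**Size for one subject.** The plan gives no figure to reproduce, so this is an illustration.

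Inputs:
- Dosing interval 28 days, 13 doses, Visit 14 being the last (protocol 4.2).
- Half-life: not in the documents. V10 (week 32) to V14 (week 48) is 16 × 7 = 112 days, which 4.7.1 equates with about 5 half-lives, so 112/5 = 22.4 days. If V9 (140 days before V14) lies outside the window, the rule fits up to 140/5 = 28 days. The assumed range is 16 to 28 days.
- Model (assumed): one compartment, linear superposition, instantaneous input.

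Formulas, with r = 2^(−28/half-life) and k = 1 for V13 up to k = 4 for V10:
- steady-state trough = r/(1 − r), in units of one dose's initial concentration;
- share of AUC(0-τ) from the dose k intervals earlier = (1 − r)r^k;
- share of the Visit 14 trough from that dose = (1 − r)r^(k−1).

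The 12 doses before V14 can be treated as an infinite series, since r^12 = 2^(−15) = 0.00003.

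At 22.4 days, r = 2^(−1.25) = 0.420:

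| Single dose missed | AUC(0-τ) | CL_ss/F | Ctrough_ss |
|---|---|---|---|
| V13 | −24.4% | +32.2% | −58.0% |
| V12 | −10.2% | +11.4% | −24.4% |
| V11 | −4.3% | +4.5% | −10.2% |
| V10 | −1.8% | +1.8% | −4.3% |

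CL_ss/F is the reciprocal of the AUC ratio, for example 1/0.756 = 1.322. Cavg_ss moves with AUC(0-τ), as does Cmax_ss in this model.

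Ro(Ctrough) with full dosing is [r/(1 − r)]/r = 1/(1 − r) = 1.73. With V13 missed it is 1.73 − 1 = 0.73, which would suggest no accumulation.

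Across 16 to 28 days, missing V13 lowers AUC(0-τ) by 21 to 25%, raises CL_ss/F by 26 to 33%, and lowers Ctrough_ss by 70 to 50%.

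**Size for the group.** The number affected is unknown. Suppose 4 of 24 mepolizumab subjects each missed one dose (an assumption; the protocol gives about 26 planned and about 20 evaluable required).
- All four at V13: geometric mean Ctrough_ss ratio 0.420^(4/24) = 0.87, a fall of 13%; CL_ss/F ratio 1.322^(4/24) = 1.05, a rise of 5%.
- One each at V10 to V13: Ctrough_ss ratio (0.420 × 0.756 × 0.898 × 0.957)^(1/24) = 0.95, a fall of 5%; CL_ss/F ratio (0.756 × 0.898 × 0.957 × 0.982)^(−1/24) = 1.02, a rise of 2%.

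**The case against.** The strongest reply is that nothing is biased unless a mepolizumab subject in the sub-study missed one of these doses, and the documents give no count. The planned summary of treatment affected by COVID-19 (SAP 6.1.1) covers the whole trial and says nothing about these subjects or visits. This stands, so the point has to be conditional.

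Second, the V13 figures are the worst case for a single miss among V10 to V13. This also stands; a miss at V10 changes AUC(0-τ) by about 2%.

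Third, the proviso that data must allow calculation, and the reference in 4.7.2 to current working practices, leave room to withhold a parameter case by case. They do, but that is discretion, not a pre-specified rule, and 4.7.1 shows that the SAP can state one.

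Fourth, affected subjects should be traceable, because concentrations, parameters, ratios and treatment interruptions are all listed, and medians and geometric means are reported. That helps a careful reader but does not correct the summary tables.

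A reader might infer that a dosing gap would be reported as an ethnic difference in exposure. The documents do not support that. The only Chinese-Caucasian comparison they describe is in the optional population PK analysis, which can model actual dosing, and SAP 4.7.2 plans no statistical tests.

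**Conclusion.** The inconsistency between 4.7.1 and 4.7.2/4.7.3 is in the text and no other section resolves it. Followed as written, the SAP would give wrong steady-state values for any subject with a missed dose in the window: AUC(0-τ), AUC(0-t), Cavg_ss, Cmax_ss, Ctrough_ss and both accumulation ratios too low, and CL_ss/F too high, as would be Vz/F if it is derived from AUC.

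Two broader conclusions would go too far. Not every parameter summarised at Visit 14 is affected: under linear PK, half-life and λz do not depend on earlier missed doses. Nor do the documents show that the Chinese exposure estimates are in fact biased, since the number of affected subjects is not given. The per-subject sizes rest on linear superposition and a half-life inferred from the SAP's look-back; the group figures rest on an assumed 4 of 24. The efficacy conclusions are not touched. This is worth correcting because the change is small and these estimates are the sub-study's endpoint.

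**What to change.** Add to SAP 4.7.2 and 4.7.3 that the main summaries of the affected parameters and ratios use subjects who meet the 4.7.1 rule:
- no missed dose at V10-V13 for Ctrough_ss and Ro(Ctrough);
- no missed dose at V10-V14 for AUC(0-τ), AUC(0-t), Cavg_ss, Cmax_ss, CL_ss/F, Vz/F if AUC-based, and Ro(Cmax).

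List all values with the excluded ones flagged, and show the all-subject summary alongside. Leave first-dose parameters, half-life and λz unchanged.

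The cost is a sentence or two, an extra set of summaries, and a few fewer subjects in the restricted tables. With about 26 planned and about 20 evaluable required, the margin is 26 − 20 = 6 before any other loss, which is a further reason to keep the all-subject summary.
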